13.2 STUDY DOCUMENTATION AND STORAGE

In accordance with federal/national regulations, ICH GCP guidelines, the Investigator must retain study records for at least 2 years after the last approval of a marketing application in an ICH region and until there are no pending or contemplated marketing applications in an ICH region or at least 2 years have elapsed since the formal discontinuation of clinical development of the investigational product. For Investigators in the European Economic Area (EEA), the study records should be maintained for at least 15 years after study discontinuation. The Investigator must notify United Therapeutics Corporation before any disposal or change in location of study records.

13.3 STUDY MONITORING AND DATA COLLECTION

In accordance with federal/national regulations, ICH GCP guidelines, monitors for United Therapeutics Corporation or its designee will periodically contact the site and conduct on-site visits. During these visits, the monitor will at a minimum: confirm ethical treatment of subjects, assess study progress, review data collected, conduct source document verification, verify drug accountability periodically, and identify any issues requiring resolution.

The Investigator must agree to allow the monitor direct access to all relevant documents and to allocate his/her time and his/her staff to the monitor to discuss any findings or any relevant issues. In addition, auditors for United Therapeutics Corporation or its designee may periodically contact the site and conduct on-site visits.

15 APPENDICES

15.1 PROCEDURE FOR 6-MINUTE WALK EXERCISE TEST AND BORG DYSPNEA SCALE

General Procedures

The 6 minute walk exercise test should be administered by the same tester and on the same course at each study site throughout the study for a given subject. The administration of the test and specifications of the testing area should be generally consistent with the American Thoracic Society guidelines and the usual practice of the investigative site [ATS guidelines; 2002].

The area used for the 6 minute walk test should be pre-measured at approximately 30 m in length (but no shorter than 15 m [16 yards or 50 feet] in length at minimum) and at least 2 to 3 m in width. There should be no turns or curves to the 6 minute walk area. The length should be marked with gradations at least every 3 meters to ensure the accurate measurement of the distance walked. The area should be well ventilated. The tester may be at the starting end of the corridor or at the midpoint of the corridor with a stop-watch. Intermittent rest periods are allowed if the subject can no longer continue. If the subject needs to rest briefly, he/she may stand or sit and then begin again when he/she is sufficiently rested but the clock will continue to run. At the end of 6 minutes, the tester will call “stop” while simultaneously stopping the watch and then measure the distance walked. The Borg dyspnea rating will be administered immediately following completion of the 6MWT.

Instructions to the Subject

Subjects will be instructed that the preceding meal should be light. Subjects should be told to wear comfortable clothing and sneakers or comfortable walking shoes. The person administering the test will use the following exact dialogue with the subject:

“The purpose of this test is to find out how far you can walk in six minutes. You will start from this point and follow the hallway to the marker (e.g. chair) at the end, turn around and walk back. When you arrive back at the starting point you will go back and forth again. You will go back and forth as many times as you can in the 6-minute period. You may stop and rest if you need to. Just remain where you are until you can go on again. However, the most important thing about the test is that you cover as much ground as you possibly can during the 6 minutes. I will

tell you the time, and I will let you know when the 6 minutes are up. When I say STOP, please stand right where you are.”

After these instructions are given to the subject, the person administering the test will then ask:

“Do you have any questions about the test?”
“Please explain to me what you are going to do.”

The person administering the test will then start the test by saying the following to the subject:

“Are you ready?”
“Start when I say “GO.”

The person administering the test will tell the subject the time at 2 and 4 minutes by saying:

“You have completed 2 minutes.”

And then by saying:

“You have completed 4 minutes.”

No other instruction or encouragement will be given during the test. Eye contact with the subject should be avoided during the test.

Following the walk, the person administering the test will obtain a rating of dyspnea using the Borg Scale. The person will use the following dialogue:

“I would like to use the following scale to indicate the maximal shortness of breath you had during the walk test (indicate the Borg Scale). If there was no shortness of breath at all you would point to 0; if the shortness of breath was not very great you would choose from 0.5 to 2; if you were somewhat more short of breath you would select 3; and if the breathing was getting very difficult, you would choose 4 to 9, depending on just how hard it was; 10 represents the greatest shortness of breath you have ever experienced in your life, and if you feel more short of breath than you have ever been in your life before, choose a number greater than 10 that represents how short of breath you feel. If one of the numbers does not exactly represent how short of breath you are, then you can choose a fraction between. For example, if you had shortness of breath somewhere between 4 and 5, you could choose 4 ½.

15.2 WHO FUNCTIONAL CLASSIFICATION FOR PULMONARY HYPERTENSION

Class I: Patients with pulmonary hypertension but without resulting limitation of physical activity. Ordinary physical activity does not cause undue dyspnea or fatigue, chest pain, or near syncope.

Class II: Patients with pulmonary hypertension resulting in slight limitation of physical activity. These subjects are comfortable at rest, but ordinary physical activity causes undue dyspnea or fatigue, chest pain or near syncope.

Class III: Patients with pulmonary hypertension resulting in marked limitation of physical activity. They are comfortable at rest. Ordinary activity causes undue dyspnea or fatigue, chest pain, or near syncope.

Class IV: Patients with pulmonary hypertension with inability to carry out any physical activity without symptoms. These subjects manifest signs of right heart failure. Dyspnea and/or fatigue may be present even at rest. Discomfort is increased by any physical activity.

15.3 CLINICAL LABORATORY PARAMETERS

Blood Chemistries	Hematology	Other
Sodium	Red Blood Cell Count	NT-proBNP (plasma)
Potassium	Hemoglobin	Urine dipstick analysis*
Chloride	Hematocrit	Urine pregnancy test**
Bicarbonate/CO ₂	Platelet Count	CD4 lymphocyte count****
Albumin	White Blood Cell Count	
Blood Urea Nitrogen/Urea		
Total Bilirubin		
Indirect Bilirubin		
Direct Bilirubin		
Alkaline Phosphatase		
Alanine Aminotransferase (ALT)		
Aspartate Aminotransferase (AST)		
Gamma-glutamyl transferase (GGT)		
Creatinine		
Thyroid Stimulating Hormone (TSH)*****		
Thyroxine (T4; free) if TSH is abnormal *****		

Visit Test Schedule

Visit	Labs Collected
Screen***	Chemistries, Hematology, TSH*****, CD4****, Urine dipstick, urine pregnancy**
Baseline***	Chemistries, Hematology, NT-proBNP, urine pregnancy**
Weeks 4 and 8	Urine pregnancy**
Week 12	Chemistries, Hematology, NT-proBNP, urine pregnancy**
Week 24	Chemistries, Hematology, NT-proBNP, urine pregnancy**
Continued Visits 1, 3 etc.	Chemistries, Hematology, NT-proBNP, urine pregnancy**
Continued Visits 2, 4, etc	Urine pregnancy**
Study Drug Termination Visit	Chemistries, Hematology, NT-proBNP, Urine dipstick, Urine pregnancy**

* pH, specific gravity, presence of protein or blood

** Urine pregnancy tests for WOCBP

*** If combining Screening and Baseline visit, utilize Baseline laboratory kit

**** At screen only; only for subjects with known HIV infection

***** If abnormal, free T4 will be automatically assessed at the central laboratory

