#### 12.5.1 *Clinical Chemistry*

The following clinical chemistry parameters will be evaluated by the central laboratory:

Parameter	Units
Sodium	mmol/L
Potassium	mmol/L
Chloride	mmol/L
Bicarbonate	mmol/L

Parameter	Units
Albumin	g/L
Blood urea nitrogen (BUN)	mmol/dL
Total bilirubin	umol/dL
Indirect bilirubin	umol/dL
Direct bilirubin	umol/dL
Alkaline phosphatase	U/L
Alanine aminotransferase (ALT/SGPT)	U/L
Aspartate aminotransferase (AST/SGOT)	U/L
Gamma-glutamyl transferase (GGT)	U/L
Creatinine	umol/L
Thyroid stimulating hormone (TSH)	mIU/L
Thyroxine (T4; free)	pmol/L

Values that are “high” or “low” with respect to the reference range provided by the central laboratory will be flagged with an “H” or an “L.” All parameters will be listed for all subjects and assessments, along with their respective “high/low” flags.

Values of these parameters at each assessment and their corresponding changes from Baseline will be descriptively summarized by treatment group.

For each parameter, the frequency and percentage of subjects within each treatment group who had “low,” “normal,” or “high” Baseline values, then subsequently had “low,” “normal,” or “high” follow-up values at each assessment will be presented in a shift summary.

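### Free T4 is measured only when TSH is abnormal, so the SAP's T4 change-from-Baseline and shift tables cannot show a new thyroid abnormality on treatment

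*Protocol*

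**What the plan says.** Protocol Appendix 15.3 has a parameter list and a visit test schedule.

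- **Parameter list.** TSH and free T4 both stand in the blood chemistry column. Free T4 is conditional: "Thyroxine (T4; free) if TSH is abnormal". The footnote gives the mechanism, with no restriction by visit: "If abnormal, free T4 will be automatically assessed at the central laboratory".
- **Visit schedule.** The Screening row names TSH separately, in addition to chemistries. Baseline, Week 12, Week 24 and the odd-numbered Continued Visits read "Chemistries, Hematology, NT-proBNP, urine pregnancy". The Study Drug Termination row also has chemistries and does not name TSH.
- **Other footnotes.** CD4 carries the note "At screen only; only for subjects with known HIV infection"; TSH does not. For combined visits: "If combining Screening and Baseline visit, utilize Baseline laboratory kit".

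Protocol 3.2.2.2 gives the laboratory visits and refers to Appendix 15.3 for the rest.

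SAP 12.5 gives a blood-sampling schedule with no exception for either analyte. SAP 12.5.1 lists TSH and free T4 like any other chemistry parameter, without the reflex condition. It then says: "Values of these parameters at each assessment and their corresponding changes from Baseline will be descriptively summarized by treatment group". It adds, for each parameter, a shift from low, normal or high at Baseline to the category at each follow-up, and a listing of all results with high/low flags. The outputs are Tables 14.3.4.1 (values and changes) and 14.3.4.2 (shifts) and Listing 16.2.8.1.

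**The concern.** Change from Baseline and shift tables need a result before dosing and a result after it. A reflex test does not supply such pairs. Whether a T4 result exists at a visit depends on the TSH result at that visit, and after dosing TSH may itself respond to treatment.

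The pattern that would suggest a thyroid effect of study drug is normal before dosing and abnormal afterwards. For T4 that pattern cannot form a pair. A reader of the T4 shift table could take the lack of normal-to-abnormal shifts as a finding, when it follows from the testing rule.

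There is also a question about the schedule. If TSH is not drawn after Screening, the SAP plans post-Baseline summaries of two analytes for which no scheduled data will exist.

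**Working it through.** No arithmetic applies. The check is to trace which results would exist for each TSH pattern and which SAP output each could enter. The SAP's Baseline window for laboratory tests (Table 8-1) takes any result up to Study Day 1 before the first dose, so a Screening TSH or T4 can serve as Baseline.

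**Reading 1: chemistries include TSH at every chemistry visit.**

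| TSH before dosing | TSH on treatment | Free T4 available | T4 values by visit and listing | T4 change and shift | TSH shift |
|---|---|---|---|---|---|
| Normal | Normal | None | No | No | Yes |
| Normal | Abnormal | On treatment only | Yes, on treatment | No | Yes: new abnormality |
| Abnormal | Normal | Before dosing only | Yes, before dosing | No | Yes: resolved abnormality |
| Abnormal | Abnormal | Both | Yes | Yes | Yes |

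Only the last row contributes to the T4 change and shift tables. New and resolved abnormalities drop out by construction, whatever their frequency. The post-dose T4 means by arm use rows two and four, that is, subjects selected because TSH was abnormal at that visit. If treatment alters how often TSH becomes abnormal, the two arms' T4 means come from differently selected subgroups and are not a randomised comparison.

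**Reading 2: TSH is drawn at Screening only.** No TSH is scheduled after dosing, so no T4 is triggered. The post-Baseline TSH and T4 values, changes and shifts are all empty. A subject with a combined Screening/Baseline visit uses the Baseline kit, whose schedule row does not name TSH, and so might have no TSH result at all.

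**Which reading is right?** The features conflict.

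- For Reading 1: TSH is in the blood chemistry column, the screen-only footnote is attached to CD4 and not to TSH, and SAP 12.5 and 12.5.1 make no exception for TSH.
- For Reading 2: the Screening row names TSH as well as chemistries, which would be redundant if chemistries already included it, and no later row names it.

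Protocol 3.2.2.2 points back to Appendix 15.3, so it does not settle the matter.

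**Result.** A new abnormality cannot enter the T4 change or shift tables under either reading. It is missing from the T4 values, the listing and the TSH shift only under Reading 2.

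**The case against.** The best answer is that TSH is the sensitive part of the pair and already has its own shift table. Under Reading 1 that table shows normal-to-abnormal TSH by arm, the new reflex T4 appears in the values table, and an out-of-range T4 is flagged in the listing. Most subjects lacking a T4 result is simply how a reflex test works. This stands, and it limits the point.

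Two stronger readings are therefore not supported. A reader might infer that a new thyroid abnormality could appear in no T4 output at all; that holds only if TSH stops at Screening, which the documents leave open. A reader might also infer that the tables would look reassuring whatever the drug does. Under Reading 1 the TSH shift would show the signal, and under Reading 2 the tables are empty, which shows absence of data and not absence of effect.

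The documents also raise no thyroid concern. The rat organ findings in Protocol 1.2.2 do not include the thyroid, Protocol 1.2.3 reports no significant laboratory changes with Remodulin, and Protocol 1.2.4 describes long-term laboratory findings on UT-15C as unremarkable. Laboratory findings judged clinically significant can be recorded as adverse events (Protocol 9.1.1) and summarised by arm (SAP 12.2). This lowers the stakes. It does not make the T4 change and shift tables interpretable, and adverse event reporting cannot pick up an abnormality on a test that was not run.

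**Conclusion.** The point holds for the T4 change and shift tables. As specified, they can contain only subjects with abnormal TSH both before and during treatment. The by-visit T4 means by arm are conditioned on a post-randomisation result. Both conclusions follow from the reflex rule and need no assumed rate.

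Whether a new abnormality is visible elsewhere depends on whether chemistries include TSH after Screening, which the documents do not settle. They also give no frequency of abnormal TSH before or during treatment, so no count of affected subjects can be stated.

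The consequence is minor: descriptive safety tables only. No hypothesis test, alpha allocation or efficacy endpoint is touched.

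**What to change.** 1. **SAP 12.5.1.** Remove free T4 from the mean, change and shift tables. Show instead, by arm, the TSH shift, with new abnormal TSH split by reflex free T4 result (low, normal, high) and all subjects with a post-dose TSH as denominator. Keep the T4 listing with its flags.
2. **Protocol Appendix 15.3.** State whether chemistries include TSH after Screening and at a combined Screening/Baseline visit, and make the SAP analyte list agree.
3. **If TSH is not run after Screening.** Either run it on the chemistry samples already drawn, or remove the post-Baseline TSH and T4 tables from the SAP.

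The cost is one clarifying sentence in the appendix, a short SAP edit and one re-specified table. Only the first option in item 3 adds an assay, and it needs no extra blood draw.

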15.4 GUIDELINES AND DEFINITIONS FOR RECORDING ADVERSE EVENTS

The Principal Investigator or a designated member of his/her staff will probe each subject for any AEs that may have occurred. The Investigator should always ask the same question when conducting the verbal probe in order to ensure uniformity between subjects. The Investigator should ask:

“How are you doing (feeling)?”

Based on the subject’s response to this question, the Investigator should ask additional questions relevant to the specific complaint such as:

“How severe is/was the symptom?”

“How often did the symptom occur?”

“How long did the symptom last?”

Using provided definitions, the Investigator will then:

(1) rate the intensity and seriousness of the AE, (2) estimate the causality of the AE to study drug, and (3) note actions taken to counteract the AE.

Definitions of Intensity, Seriousness, Causality, Action Taken, and Outcome

INTENSITY

An assessment of the relative intensity (severity) of an AE is based on the Investigator’s clinical judgment. The maximum intensity encountered during the evaluation period should be checked. The assessment of intensity should be independent of the assessment of the seriousness of the AE.

SERIOUSNESS

A serious AE is one that represents an actual or potential significant hazard. This includes, but is not limited to, an event that is fatal, life-threatening, permanently or severely disabling, requires or prolongs inpatient hospitalization, is a congenital abnormality (offspring of subject) or is medically significant (important medical events that may not result in death, be life-threatening, or require hospitalization may be considered a serious AE when, based upon appropriate medical

judgment, they may jeopardize the subject and may require medical or surgical intervention to prevent one of the outcomes listed in this definition).

CAUSALITY

An estimate of causality between a specified AE and the study drug is made by the Investigator. Definitions of the categories follow:

- NOT RELATED - there is not a temporal relationship to study drug administration (too early, or late, or study drug not taken), or there is a reasonable causal relationship between another drug, or concurrent disease and the SAE
- POSSIBLE - there is a reasonable causal relationship between the study drug and the SAE. Dechallenge information is lacking or unclear
- PROBABLE - there is a reasonable causal relationship between the study drug and the SAE. The event responds to dechallenge. Rechallenge is not required

ACTION TAKEN

TEST AGENT DOSE MODIFICATION*

- Dose Increased - the dose or regimen of the test agent was increased
- Dose Not Changed - the dose or regimen of the test agent was not changed
- Dose Reduced - the dose or regimen of the test agent was decreased
- Drug Interrupted - administration of the test agent was stopped temporarily
- Drug Withdrawn - administration of the test agent was stopped permanently and not restarted
- Unknown - changes to the administration of the test agent cannot be determined

*NOTE: Only the last test agent action should be recorded in the eCRF.

OUTCOME

- Fatal - The study subject died
- Not Recovered/Not Resolved - The AE was ongoing
- Recovered/Resolved - The AE resolved
- Recovered/Resolved with Sequelae - The AE is considered resolved however there is a residual sequelae
- Recovering/Resolving - The AE is improving but is not yet completely recovered/resolved
- Unknown - The outcome of the AE cannot be determined

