1.4 CLINICAL HYPOTHESIS

The hypothesis of this study is that treatment with oral UT-15C combined with PAH-approved oral monotherapy as compared with placebo with PAH-approved oral monotherapy will:

- Delay time to first clinical worsening (morbidity or mortality) event

The hypothesis for the change of dosing frequency from BID to TID is that delivering more sustained concentrations of treprostinil may allow for systemic exposure to drug that more closely resembles the approved parenteral product, Remodulin, and reduce the occurrence of PGI₂ AEs previously seen with the BID regimen. Both of these improvements may allow study subjects to titrate to a more effective UT-15C dose and thus study drug may show a clinically and statistically significant difference compared to placebo in delaying time to first clinical worsening.

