frequent telephone calls may be necessary depending on the frequency of dose titration and to manage AEs or signs and symptoms of disease. If dose titration is considered appropriate, site personnel will instruct the subject to modify their dose. Study drug dosing should be recorded at each study visit between Baseline and Week 24. Dose changes between Baseline and Week 24 will be recorded in source documentation and the subject's eCRF by site personnel. Beyond Week 24, study drug dose will be recorded on the day of Continued Visits (e.g. Weeks 36, 48, etc.) and every 30 days between Continued Visits in source documentation and the eCRF by site personnel. If it becomes necessary for a subject to modify their dose (e.g., due to an AE) without prior instructions from site personnel, the subject should be instructed to contact the site as soon as possible and report any dose changes to site personnel for updating in source documentation and the eCRF as appropriate.

After Week 24, at least monthly telephone calls should be made to continue to monitor AEs and make decisions regarding appropriate dose titrations. More frequent telephone calls may be necessary depending on the frequency of dose titration and to manage AEs or signs and symptoms of disease. Site personnel should record all dose changes in source documentation from Week 24 until Study Termination.

In the event a subject requires to be permanently discontinued from study drug (e.g. as a result of clinical worsening or the subject wishes to withdraw from further participation in the study), the Investigator should conduct the study drug termination assessments and then gradually down titrate the study drug, taking into consideration the subject's clinical condition, current study drug dosing regimen, and previous clinical response to study drug.

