Throughout the course of the study, the dose of study drug should continue to be increased at the discretion of the Investigator up to a maximum allowable dose of 12 mg TID. Dose escalation may be made less frequently or temporarily suspended if a subject experiences an intolerable AE that may worsen as a result of an increase in study drug dose. If an AE remains intolerable, the Investigator may decrease the dose of study drug. In the event of continued intolerable AEs, dose reductions may occur. The exact dose reduction and frequency of dose reduction should be based on the clinical condition of the subject and the severity/seriousness of the event. In general, dose reductions may occur in 0.125 mg or 0.25 mg increments every 12 to 24 hours.

Larger dose reductions may be necessary in the event of an emergency situation. If the subject is still experiencing an intolerable AE then the Investigator may temporarily or permanently withdraw the subject from study drug. Following temporary discontinuation of study drug, all attempts should be made to re-initiate study drug in affected subjects. Subjects should be re-started on study drug at a reduced dose or at 0.125 mg TID depending on the clinical condition of the subject, the subject's previous response to study drug, the dose at the time of discontinuation, and the duration of temporary discontinuation from study drug. Following restart of study drug, all efforts should be made to increase the dose until the desired clinical improvement in the subject's symptoms of PAH occurs.

Notwithstanding these study drug dosing guidelines, the well-being of each subject is paramount and all Investigators must act in accordance with the best medical interests of the subjects at all times during their participation in the study.

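### The adverse event page keeps only the last study-drug action, so it cannot reliably count AEs that led to dose reduction or interruption, and the SAP plans no such table

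*Protocol*

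**What the plan says.** Protocol Appendix 15.4 has the investigator rate each AE, judge causality and "note actions taken to counteract the AE". The dose-action field offers *Dose Increased*, *Dose Not Changed*, *Dose Reduced*, *Drug Interrupted*, *Drug Withdrawn* and *Unknown*. A note under the list limits the entry: "Only the last test agent action should be recorded in the eCRF". For intensity, the same appendix keeps the worst value rather than the latest: "The maximum intensity encountered during the evaluation period should be checked".

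Protocol Section 6.1 lets the investigator slow or suspend escalation, reduce the dose, or stop study drug temporarily or permanently for an intolerable AE. On what follows a temporary stop, it says: "Following temporary discontinuation of study drug, all attempts should be made to re-initiate study drug in affected subjects". It then says: "Following restart of study drug, all efforts should be made to increase the dose until the desired clinical improvement".

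Dosing is also recorded separately from AEs. Section 6.1 states: "Dose changes between Baseline and Week 24 will be recorded in source documentation", and in the eCRF as well. For the later period: "Beyond Week 24, study drug dose will be recorded on the day of Continued Visits", and every 30 days between those visits, in both places. From Week 24 to study termination, the requirement to record all dose changes names source documents only.

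SAP Section 12.1 lists the dose and date of each change. SAP Section 12.2 lists every AE with all its eCRF details. The only AE output tied to a dose action, in Section 12.2 and in the table list in Section 16.1, is discontinuation of study drug (Table 14.3.1.8 and its listing, 14.3.2.3).

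**The concern.** Study drug in this trial is titrated throughout and may be reduced, stopped, restarted and raised again. An AE can therefore carry more than one dose action. A field that keeps only the last can show how the episode ended and lose the step the AE forced.

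What is at stake is a direct measure of AE-limited dosing. Protocol Section 1.4 argues that three-times-daily dosing should bring steadier exposure and fewer prostacyclin-type AEs, and adds: "Both of these improvements may allow study subjects to titrate to a more effective UT-15C dose". How often an AE forced a reduction or an interruption, by arm, bears directly on that argument. As written, the AE page cannot answer the question reliably, and the SAP does not ask it.

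**Working it through.** The plan states no figure on this point, so there is none to reproduce. The check traces one AE through the AE page, the dose record and the planned outputs.

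**1. AE page.** Take a single AE that is still open while study drug is changed, and apply the note in Appendix 15.4.

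| Course of the AE | Value stored | What the AE page no longer shows |
|---|---|---|
| Reduced, then interrupted | *Drug Interrupted* | the reduction |
| Interrupted, then restarted at a lower dose | *Dose Reduced*, if the restart is coded as an action for the AE | the interruption |
| Reduced or interrupted, then escalated again | *Dose Increased*, if the later increase is coded as an action for the AE | the reduction or interruption |
| Any course ending in a permanent stop | *Drug Withdrawn* | earlier steps; the withdrawal itself is kept |

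The first row needs no special reading of the note. The second and third depend on what a site counts as an action taken for the AE, which Appendix 15.4 does not settle. About 150 centers (Protocol Section 3.3) could settle it differently.

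**2. Dose record.** Up to Week 24 each change is in the eCRF, so the change survives. Neither Protocol Section 6.1 nor the listing in SAP Section 12.1 names a reason or a linked AE, so what is lost is the attribution. After Week 24 the required eCRF entries are the Continued Visit doses and the 30-day doses. Section 6.1 allows reductions every 12 to 24 hours, so a short reduction or stop can begin and end between two required entries. Source documents should still hold it.

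**3. Planned outputs.** SAP Sections 12.2 and 16.1 plan AE incidence, rate per patient-year, seriousness, maximum intensity, causality, dose at onset and permanent discontinuation. Only the last uses a dose action. Appendix 15.4 defines withdrawal as a permanent stop with no restart, so no later titration can replace it. No planned summary table draws on an overwritten value; the AE listing does show the stored value.

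**4. Size, if a count were made from this field.** Let *N* be the number of AEs in an arm that led to an interruption without a later permanent stop, and *s* the share for which a later action was stored instead.

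- Count obtained = *N* × (1 − *s*).
- With *s* = 0 the count is *N*; with *s* = 1 it is 0.
- The ratio of UT-15C to placebo counts is multiplied by (1 − *s* on UT-15C) / (1 − *s* on placebo), so the comparison is distorted whenever the two shares differ.

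The documents give no value for *s* in either arm, so the full range from 0 to 1 stays open. Reductions can be lost in the same way, although interruptions relabelled as reductions at restart would add some back.

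**The case against.** The strongest reply is that nothing the SAP plans to tabulate is harmed. That stands. A reader might infer that the trial's reported tolerability will be understated; the documents do not support this, because the summary tables do not use the values that can be overwritten and permanent withdrawal is preserved.

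A reader might also infer that AE-driven dose changes are erased. They are not. Up to Week 24 they are in the eCRF, and afterwards they are required in source documents. Section 6.1 also asks for eCRF updating, as appropriate, when a subject changes the dose without prior instruction, and SAP Section 12.1 promises each change with no Week 24 cut-off. The loss is the link to the AE and, after Week 24, possibly the eCRF record of short changes.

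A third tempting inference is that a forced reduction will routinely be stored as *Dose Increased*. That depends on reading renewed escalation as something done to counteract the AE, which is arguable. The steps in Section 6.1 for reducing or stopping are also discretionary, so no fixed sequence can be assumed. Even on the narrow reading, however, a reduction followed by an interruption loses the reduction.

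Finally, earlier-trial figures might be offered as a measure of the loss: AE discontinuations of 14% against 5% in TDE-PH-301, and mean maximum doses of 3.1 mg against 6.1 mg twice daily in TDE-PH-308 (UT-15C against placebo; Protocol Section 1.2.4). Neither is one. The first counts permanent stops, which the rule keeps. The second comes from dosing data, and the protocol does not attribute that gap to AEs. Neither counts AEs with more than one dose action.

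**Conclusion.** The point holds as a minor data-capture weakness. The AE page cannot give a reliable count of AEs leading to dose reduction or interruption, the dose record does not replace that count because no reason or linked AE is named, and the SAP plans no table of it. The AE listing may show a last action that hides the one the AE required.

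The conclusion assumes that the eCRF follows Appendix 15.4 as written and has no reason-for-change field that the protocol and SAP leave unmentioned. The size of the loss is unknown. The primary analysis, the sample size and the planned AE incidence, intensity, causality and permanent-discontinuation tables are not affected.

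**What to change.** In Protocol Appendix 15.4, replace the note with an instruction to record every study-drug action taken for the AE. If the form can hold only one value, record the most restrictive, in the order Withdrawn > Interrupted > Reduced > Not Changed > Increased. This matches the worst-value approach already used for intensity and changes recording only, not dosing.

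In SAP Sections 12.2 and 16.1, add two tables by arm beside Table 14.3.1.8: AEs leading to interruption of study drug, and AEs leading to dose reduction.

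The cost is a small eCRF change, one revised instruction to sites and two extra tables. For AEs already entered, earlier actions could be inferred only from the timing of dose changes. Such entries should be flagged as inferred, and they will be weaker after Week 24 unless source documents are consulted.
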